9.3.2. Primary Endpoint(s)/Estimand(s) Analysis

9.3.2.1. Safety Analysis

The safety data will be summarized in accordance with Pfizer Data Standards. All participants who receive study intervention (safety population) will be included in the safety analyses. All safety data will be summarized descriptively through appropriate data tabulations, descriptive statistics, categorical summaries, and graphical presentations. Safety endpoints for the study include:

- Treatment-emergent AEs and SAEs;
- Withdrawals from active treatment due to AEs;
- Clinical laboratory tests (eg, hematology [including coagulation panel], chemistry and urinalysis);
- ECG changes from baseline;
- Vital signs.

Change from baseline on laboratory data and vital signs will be additionally summarized. Participant listings will also be produced for these safety endpoints.

AEs, ECGs, BP, PR, and safety laboratory data will be reviewed and summarized on an ongoing basis during the study to evaluate the safety of participants. Any clinical laboratory, ECG, BP, and PR abnormalities of potential clinical concern will be described. Safety data

will be presented in tabular and/or graphical format and summarized descriptively, where appropriate.

Medical history and PE and neurological examination information, as applicable, collected during the course of the study will be considered source data and will not be required to be reported, unless otherwise noted. However, any untoward findings identified on physical and/or neurological examinations conducted during the active collection period will be captured as AEs, if those findings meet the definition of an AE. Data collected at Screening that are used for inclusion/exclusion criteria, such as laboratory data, ECGs, and vital signs, will be considered source data, and will not be required to be reported, unless otherwise noted. Demographic data collected at Screening will be reported.

9.3.2.1.1. Electrocardiogram Analyses

Changes from baseline for the ECG parameters QT interval, heart rate, QTc interval, PR interval, and QRS complex will be summarized by treatment and time.

The number (%) of participants with maximum postdose QTc values and maximum increases from baseline in the following categories will be tabulated by treatment:

Safety QTc Assessment

Degree of Prolongation	Mild (msec)	Moderate (msec)	Severe (msec)
Absolute value	>450-480	>480-500	>500
Increase from baseline		30-60	>60

If more than 1 ECG is collected at a nominal time after dose administration (for example, triplicate ECGs), the mean of the replicate measurements will be used to represent a single observation at that time point. If any of the 3 individual ECG tracings has a QTc value >500 msec, but the mean of the triplicates is not >500 msec, the data from the participant's individual tracing will be described in a safety section of the CSR in order to place the >500 msec value in appropriate clinical context. However, values from individual tracings within triplicate measurements that are >500 msec will not be included in the categorical analysis unless the average from the triplicate measurements is also >500 msec. Changes from baseline will be defined as the change between the post-dose QTc value and the average of the time-matched baseline triplicate values on Day 1, or the average of the pre-dose triplicate values on Day 1.

In addition, an attempt will be made to explore and characterize the relationship between plasma concentration and QT interval length using a PK/PD modeling approach. If a PK/PD relationship is found, the impact of participant factors (covariates) on the relationship will be examined. Details of said model and analyses will be elucidated in an analysis plan separate from the SAP.

9.3.2.2. Change in NT-proBNP

9.3.2.2.1. Main Analysis

- Estimand strategy: Hypothetical (Section 9.1.1).
- Analysis set: PD-Biomarker Analysis (Section 9.2).
- Analysis methodology: Change from baseline relative to placebo will be analyzed using a linear mixed model including data from Weeks 4, 8, 12, 16, 20 and 24 with treatment and time and fixed effect (Section 9.3.1) with subject (and/or time) as a random effect and an unstructured covariance matrix for random effects ie, a random intercepts and slopes model. If the above model does not converge, random intercepts and slope models with different covariance matrix specifications (eg, compound symmetry) will be tried.
- Intercurrent events and missing data: Data after study drug discontinuation and rescue will be excluded; intermediate missing values will not be imputed.
- The sample size, mean, standard deviation, median, minimum, and maximum at the baseline and postbaseline visits for observed NT-proBNP and change from baseline will be presented for treatment and placebo.
- The least-squares (LS) means, the 95% confidence interval for the LS means, the difference between the LS means for each treatment arm, and the corresponding 95% confidence interval will be presented for change from baseline in NT-proBNP for all post-baseline visits.

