9.1.2. Part B

NT-proBNP Endpoint

Null hypothesis for NT-proBNP for Part B of this study is that the mean observed NTproBNP change from baseline at 24 weeks in PAH patients on PF-07868489 is no different than the mean observed NT-proBNP change from baseline at 24 weeks in PAH patients on placebo. The alternative hypothesis is that mean NT-proBNP levels decline from baseline at 24 weeks for PAH patients on PF-07868489 relative to PAH patients on placebo.

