9.1.3.1. Primary Estimand/Coprimary Estimands

E1 (primary analysis estimand): The estimand is the difference between the PF-07868489 and placebo in mean change from baseline in NT-proBNP at Week 24 in PAH patients. This analysis will utilize the Hypothetical approach, excluding data after use of rescue medications prior to week 24 and after study treatment discontinuation.

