9.3.1.1. Analyses for Longitudinal Continuous Endpoints

Linear mixed models will be used. The fixed effects of treatment, visit, and treatment-byvisit interaction will be included. Visit will be modeled as a categorical covariate. Unstructured covariance matrix will be assumed for the model errors. If the above model does not converge, random intercepts and slopes models with different covariance matrix specifications (eg, compound symmetry) will be tried. Moreover, a visit could be treated as a continuous covariate. Details regarding additional specifications will be described in the SAP.

When modeling the change from baseline values, the variable for visit will start with the first post-baseline visit. At each visit, estimates of least square mean (LSM) values and the LSM differences between treatment groups will be derived from the model. The corresponding p-values and 95% confidence intervals will also be derived from the model.

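### Sections 9.3.1.1 and 9.3.2.2.1 specify different primary NT-proBNP models, and the second, read literally, has no treatment-by-visit term to give the Week 24 difference

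*Protocol*

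**What the plan says.** The target is a Week 24 quantity. Protocol Section 9.1.3.1 defines E1 as the difference between arms "in mean change from baseline in NT-proBNP at Week 24 in PAH patients", and the alternative hypothesis in Section 9.1.2 is also set at 24 weeks.

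Section 9.3.1.1 gives the general longitudinal model: "The fixed effects of treatment, visit, and treatment-byvisit interaction will be included. Visit will be modeled as a categorical covariate". On covariance it says: "Unstructured covariance matrix will be assumed for the model errors". Random coefficients come second: "If the above model does not converge, random intercepts and slopes models with different covariance matrix specifications (eg, compound symmetry) will be tried". It also allows visit to be treated as continuous.

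Section 9.3.2.2.1, the main analysis of the primary endpoint, describes a linear mixed model on the six four-weekly visits from Week 4 to Week 24. Its terms are set out as follows: "with treatment and time and fixed effect (Section 9.3.1) with subject (and/or time) as a random effect and an unstructured covariance matrix for random effects". The section glosses this as a random-coefficients model, with a random intercept and a random slope. Its fallback is another random intercepts and slopes model with a different covariance. It then promises LS-mean differences with confidence intervals for every post-baseline visit.

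**The concern.** These are two written specifications of one primary analysis, and the fallback in one is the main model in the other. They differ on the model type, on where the unstructured matrix sits and on the listed fixed effects. The primary estimate and p-value can therefore depend on which section is followed.

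The fixed effects matter most. Without a treatment-by-visit term the model has a single treatment coefficient, a weighted average of the differences at Weeks 4 to 24. If the effect builds over time, that average is smaller than the Week 24 difference. Gradual onset fits the protocol's own rationale: Sections 2.2 and 4.2.2 expect benefit through pulmonary vascular remodelling and eventual improvement in right ventricular haemodynamics.

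**Working it through.** **The two specifications side by side**

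| Feature | Section 9.3.1.1 | Section 9.3.2.2.1 |
|---|---|---|
| Fixed effects listed | treatment, visit, treatment-by-visit | treatment, time |
| Form of time | categorical (continuous allowed as an alternative) | not stated |
| Unstructured matrix applies to | model errors | random effects |
| Random intercepts and slopes | fallback | main model |
| First visit | first post-baseline visit (Week 1 in the schedule of activities) | Week 4 |

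Section 9.3.2.2.1 also conflicts with its own output. With no interaction, the LS-mean difference is the same number at every visit, so reporting it by visit would serve no purpose.

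**The plan's own figure.** Section 9.5 gives 36 randomised for 30 evaluable with 15% dropout: 30/0.85 = 35.3, rounded up to 36, which agrees. The power of more than 90% cannot be reproduced because no standard deviation is stated. The contradiction does not depend on it.

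**What the no-interaction coefficient estimates.** Let d(t) be the true difference at week t, scaled so that d(24) = 1. With complete data and time effects common to both arms, the coefficient targets Σ w(t)·d(t), where w = V⁻¹1/(1′V⁻¹1) and V is the within-subject covariance over the six visits. The onset shapes and V below are assumptions; the protocol gives neither.

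*Equal weights (compound symmetry, each 1/6)*
- Linear onset, d(t) = t/24: (4+8+12+16+20+24)/(6×24) = 84/144 = 0.58.
- Exponential onset, d(t) = (1−e^(−t/8))/(1−e^(−3)): (0.414+0.665+0.818+0.910+0.966+1)/6 = 0.80.
- Full effect from Week 4: 1.00, so nothing is lost.

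*Random-slope weights* (intercept variance 0.10, residual variance 0.10, time scaled as t/24, intercept and slope uncorrelated)

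| Slope variance | Weights, Weeks 4 to 24 | Linear onset | Exponential onset |
|---|---|---|---|
| 0.05 | 0.26, 0.23, 0.19, 0.15, 0.11, 0.07 | 0.47 | 0.72 |
| 0.15 | 0.38, 0.29, 0.21, 0.12, 0.04, −0.04 | 0.34 | 0.63 |
| 0.30 | 0.46, 0.34, 0.23, 0.11, −0.01, −0.13 | 0.24 | 0.56 |

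With slope variance 0.30 and residual variance cut to 0.02, linear onset gives 0.07. Random slopes move weight to the early visits, and Week 24 can receive none or negative weight.

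*In percentage terms.* If the 45% in Section 9.5 is read as a 45% reduction relative to placebo on the log scale, the targeted reduction is 1 − 0.55^ratio. For linear onset this is 29% with equal weights, and 24%, 18% and 13% in the three random-slope rows.

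**If the interaction is kept but time is linear.** The Week 24 value is then a straight-line prediction. It is exact for linear onset. An ordinary least-squares line through the exponential curve predicts 1.076 at Week 24, an overstatement of about 8%.

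**The case against.** The best defence is that the interaction is intended. The reference to Section 9.3.1 sits directly after the fixed effects in Section 9.3.2.2.1, so it can be read as importing that section's treatment, categorical visit and treatment-by-visit terms. The by-visit LS-mean differences make sense only on that reading. The Week 24 contrast would then target E1 under either covariance model, and none of the dilution figures would apply. This is a fair reading, so a reader should not infer that the protocol has definitely dropped the interaction. It does not remove the conflict, because the section it points to treats random intercepts and slopes as the fallback and puts the unstructured matrix on the errors.

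It can also be said that the SAP will settle this, since Section 9.3 has it finalised before any analyses. Section 9.3.1.1 does leave further model details to the SAP. But this is a contradiction between two stated models, not a missing detail, and Section 9 says major changes to primary endpoint analyses will also appear in a protocol amendment.

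A reader might infer that power falls from 90% to about 47%. That figure multiplies a standardised effect of 1.226 (90% power, 15 per arm, two-sided 0.05) by 0.58 and keeps the standard error of a single visit. Averaging six visits shrinks the standard error by √((1+5ρ)/6) under compound symmetry. Power with linear onset is then 83%, 70%, 59% and 52% at assumed between-visit correlations of 0.3, 0.5, 0.7 and 0.85. A reader might also infer that random-slope weighting always removes nearly all of the effect; ratios near 0.1 need particular variance components.

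Finally, an unstructured 6×6 matrix has 21 parameters for about 30 evaluable participants, so non-convergence is a real possibility and a fallback is needed. A random-coefficients covariance is acceptable in that role if categorical visit and the interaction stay.

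**Conclusion.** The concern stands as a contradiction within the protocol over the primary model. That conclusion rests on the text alone.

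The numerical consequence is conditional. If Section 9.3.2.2.1 is followed literally, without an interaction, and the effect builds over time, the treatment coefficient is 0.58 or 0.80 of the Week 24 effect with equal weights, for linear or exponential onset. With random-slope weights and linear onset it is roughly 0.1 to 0.5. If the effect is constant from Week 4, or the interaction is included with categorical visit, there is no dilution. The documents do not support the stronger claim that the primary analysis cannot estimate the Week 24 effect. They leave open whether it will, and that should be closed before analysis.

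**What to change.** In Section 9.3.2.2.1, name one primary model: fixed effects of treatment, categorical visit and treatment-by-visit, with the unstructured residual covariance of Section 9.3.1.1. State that the primary test is the treatment contrast at Week 24. Require any non-convergence fallback to keep categorical visit and the interaction and to change only the covariance structure. Remove the continuous-visit option for the primary analysis, and present random intercepts and slopes, if kept, only as such a fallback. Confirm that Weeks 4 to 24 are the visits used.

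The degrees-of-freedom method and the order of fallback covariance structures can be left to the SAP. The cost is protocol and SAP wording only, with no change to data collection, visits or sample size.

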9.3.3. Secondary Endpoint(s)/Estimand(s) Analysis

9.3.3.1. Change in PVR

9.3.3.1.1. Main Analysis

- Estimand strategy: Hypothetical (Section 9.1.1).
- Analysis set: PD-Hemo Analysis (Section 9.2).
- Analysis methodology: Observed PVR of treatment relative to placebo will be analyzed using a linear mixed model including data from Pre-baseline and Week 24 with treatment and time and fixed effect (Section 9.3.1) with subject (and/or time) as a random effect and an unstructured covariance matrix for random effects ie, a random intercepts and slopes model.
- Intercurrent events and missing data: Data after study drug discontinuation and rescue will be excluded; intermediate missing values will not be imputed.
- The sample size, mean, standard deviation, median, minimum, and maximum at the baseline and postbaseline visits for observed NT-proBNP and change from baseline will be presented for treatment and placebo.

• The least-squares (LS) means, the 95% confidence interval for the LS means, the difference between the LS means for each treatment arm at each visit, and the corresponding 95% confidence interval will be presented.

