9.1.3.2. Secondary Estimands

E2 (secondary efficacy estimand): The estimand is the difference between the PF-07868489 and placebo in mean change from baseline in PVR at Week 24 in PAH patients. This analysis will exclude data after use of rescue medications and after study treatment discontinuation.

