9.2. Analysis Sets

For purposes of analysis, the following analysis sets are defined:

Participant Analysis Set	Description
Enrolled	"Enrolled" means a participant's or their legally authorized representative's, agreement to participate in a clinical study following completion of the informed consent process.
PK Population	The PK concentration population is defined as randomized participants who received at least one dose of PF- 07868489 and have at least 1 evaluable concentration. The PK parameter population is defined as all randomized participants who received at least one dose of PF- 07868489 and have at least 1 evaluable PK parameter
PD-Biomarker Population	The PD-Biomarker population is defined as all randomized participants treated who have at least one evaluable NT- proBNP result
PD-Hemodynamic	The PD-Hemodynamic population is defined as all randomized participants treated who have at both PVR measurements (pre- and post-baseline)
Safety analysis set	All participants randomly assigned to study intervention and who take at least 1 dose of study intervention. Participants will be analyzed according to the product they actually received.
Per-protocol Population	All PAH patients in the PD population with no PIPDs. Patients will be analyzed according to randomized treatment assignment.

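### PVR main analysis: the random intercept-and-slope structure cannot be identified from two measurements, and the listed Week 24 output is neither E2's difference in change nor adjusted for baseline PVR

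*Protocol*

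**What the plan says.** Section 9.3.3.1.1 takes observed PVR as the response: "Observed PVR of treatment relative to placebo will be analyzed using a linear mixed model including data from Pre-baseline and Week 24 with treatment". It names time as the other fixed effect and points to Section 9.3.1. The random part is "with subject (and/or time) as a random effect and an unstructured covariance matrix for random effects ie, a random intercepts and slopes model". The section then promises LS means, their difference between arms at each visit, and 95% confidence intervals. Its descriptive-summary bullet refers to NT-proBNP, not PVR.

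The target is E2 in Section 9.1.3.2: "the difference between the PF-07868489 and placebo in mean change from baseline in PVR at Week 24 in PAH patients".

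Section 8.2.1 and the Part B schedule place right heart catheterisation at Screening and Week 24. The PD-Hemodynamic set in Section 9.2 is "all randomized participants treated who have at both PVR measurements (pre- and post-baseline"), so every participant analysed contributes exactly two values.

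The general text in Section 9.3.1.1 includes treatment, visit and treatment-by-visit, and places an unstructured matrix on the model errors. If that model does not converge, it falls back to random intercepts and slopes with other covariance structures.

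**The concern.** There are two separate problems.

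1. **Covariance structure.** The PVR bullet uses the same random-effects wording as the NT-proBNP bullet in Section 9.3.2.2.1. NT-proBNP has six post-baseline visits in its model, which can support a random intercept, a random slope and residual error. PVR has two time points, which cannot. The PVR section also lacks the convergence fallback that the NT-proBNP section has.

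2. **Output against estimand.** E2 is a difference in change. The listed output is a difference in observed PVR at each visit. These are different statistics, and the one listed ignores each participant's baseline value.

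PVR is the only secondary efficacy endpoint with a stated estimand. At stake are a programme that may not run cleanly, an analyst left to improvise after unblinding, and avoidable loss of precision in a small study.

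**Working it through.** The protocol gives no power, SD or correlation for PVR, so there is no stated figure to reproduce.

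**Step 1: parameter count.** Inputs: two PVR values per participant (Sections 8.2.1 and 9.2) and the random structure in Section 9.3.3.1.1. Code time as 0 and 1. Let g11, g12, g22 be the intercept variance, the covariance and the slope variance, and s² the residual variance.

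- Var(first) = g11 + s²
- Cov(first, second) = g11 + g12
- Var(second) = g11 + 2·g12 + g22 + s²

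That is 4 parameters and 3 distinct moments. Add d to s² and to g12, subtract d from g11 and subtract 2d from g22. The changes are then:

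- Var(first): −d + d = 0
- Cov: −d + d = 0
- Var(second): −d + 2d − 2d + d = 0

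Infinitely many parameter sets therefore give the same likelihood. The matrix of derivatives has rank 3 for two visits. For the same structure over NT-proBNP Weeks 4 to 24 it has rank 4, so that model is identified.

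**Step 2: what non-identification does to the result.** One data set was simulated with 15 per arm, unit SDs and a correlation of 0.6, and the model included treatment-by-visit. These settings are illustrative.

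| Residual variance fixed at | REML log-likelihood | Treatment-by-visit | SE |
|---|---|---|---|
| 0.01 | −18.797385 | −0.722 | 0.282 |
| 0.1 | −18.797385 | −0.722 | 0.282 |
| 0.2 | −18.797385 | −0.722 | 0.282 |

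The likelihood is flat. The contrast and its SE do not move, and they equal the two-sample difference in mean change (−0.722, SE 0.282). The damage is confined to the variance components and to numerical behaviour.

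**Step 3: what the listed Week 24 output is.** Take the favourable reading, with treatment-by-visit included. With complete pairs and free baseline means in each arm, the Week 24 LS mean in each arm is the simple Week 24 average. Their difference is the raw Week 24 difference. E2's difference in change equals that figure minus the observed baseline difference. The two agree in expectation under randomisation, but not in any one data set. With 15 per arm (the evaluable number in Section 9.5, set for NT-proBNP), the baseline difference has a standard error of √(2/15) = 0.37 SD.

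**Step 4: precision.** Let σ be a common SD at both visits, n the number per arm and r the baseline-to-Week-24 correlation. The values of r are assumed.

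- Raw Week 24 difference: SE = σ·√(2/n)
- ANCOVA: SE ≈ σ·√(1 − r²)·√(2/n)
- Ratio = 1/√(1 − r²)

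| Assumed r | √(1 − r²) | SE ratio, raw to ANCOVA |
|---|---|---|
| 0.5 | 0.866 | 1.15 |
| 0.7 | 0.714 | 1.40 |
| 0.8 | 0.600 | 1.67 |

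**The case against.** The strongest reply is that the estimate and its interval are unaffected by the redundant parameter, as Step 2 shows, and variance components are not a planned output. That stands, and it limits the first problem to failed or singular fits.

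It can also be said that the protocol leaves identified models within reach. The and/or wording would allow a random intercept alone. The default in Section 9.3.1.1, an unstructured matrix on the errors without random effects, is identified. Compound symmetry on the random effects gives 2 + 1 = 3 parameters and is also identified for two visits. But the PVR bullet resolves its own and/or by naming "an unstructured covariance matrix for random effects ie, a random intercepts and slopes model". Adding the unstructured error matrix to that gives 3 + 3 = 6 parameters for 3 moments. The compound-symmetry option appears in the general section and not in the PVR section. None of this changes the listed output, so the second problem is untouched.

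The SAP may add detail, but the protocol has itself fixed this model and this output. PVR is secondary, no hypothesis is stated for it and Part B was not sized on it. That bears on severity, not on whether the text is right.

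A reader might also infer that, because the bullet names only treatment and time, the reported effect is a treatment main effect averaged over both visits and so diluted, to half the Week 24 effect if the variances are equal. The documents do not support this. The bullet refers to Section 9.3.1, where treatment-by-visit is included, and the planned result is a difference at each visit. With the interaction fitted, the Week 24 difference recovers the full effect.

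**Conclusion.** The point holds and should be fixed.

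- The specified covariance structure is not identified for PVR: 4 parameters, 3 moments. This follows from the design and needs no assumption. Its effect is numerical, not a bias in the treatment contrast.
- The listed Week 24 output is the raw difference in observed PVR. It is unbiased under randomisation, but it is not E2's difference in mean change and it takes no account of baseline PVR. This rests on complete pairs, which Section 9.2 requires, and on baseline means that are not constrained equal.
- The precision cost is an SE about 1.15 to 1.7 times that of ANCOVA for r from 0.5 to 0.8 with equal SDs. That range is an assumption.
- The NT-proBNP wording in the PVR summary bullet leaves this section without a descriptive summary of PVR.

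It would go too far to conclude that the planned PVR result would be arbitrary or shrunk toward zero. Nor do the documents call for a log transformation: E2 is a difference in mean change, and a ratio of PVR would be a different estimand.

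**What to change.** In Section 9.3.3.1.1:

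1. Delete the random intercept and slope text.
2. Specify ANCOVA of change from baseline in PVR at Week 24 on treatment and baseline PVR, on the original scale so that it targets E2. An essentially equivalent alternative is a two-visit model with visit and treatment-by-visit, baseline means constrained equal across arms, an unstructured 2×2 residual covariance (3 parameters for 3 moments) and no random effects.
3. State that the Week 24 treatment contrast, with its 95% confidence interval, is the estimate of E2.
4. Replace NT-proBNP with PVR in the summary bullet.

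The cost is wording in the protocol, with the SAP aligned to it. No visit, measurement, sample size or estimand changes, and the analysis is simpler to program.
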